4.2 Inclusion Criteria

Subjects will be included in the study if they are or have:

- Willing and able to understand and sign the study specific Informed Consent Form (ICF) approved by the site's Institutional Review Board (IRB)/Independent Ethics Committee (IEC)
- 2. Pathologically-confirmed squamous cell carcinoma of the oral cavity, oropharynx, nasopharynx or hypopharynx or unknown primary HPV-positive tumor presumed to be of oropharyngeal, nasopharyngeal or hypopharyngeal origin.
- 3. Tumor HPV status established
- 4. Planned to receive either primary or post-operative CRT
- 5. Planned IMRT as single daily fractions of 2.0 to 2.2 Gy with a cumulative radiation dose of at least 50 Gy and maximum dose of 72 Gy
- 6. The radiation field must provide for a minimal cumulative dose of 50 Gy to at least two sites at risk for OM (maxillary or mandibular labial mucosa, right or left buccal mucosa, right or left ventral and/or lateral tongue, floor of oral cavity, or soft palate/tonsillar pillars)
- 7. Planned administration of cisplatin administered at a dose of 30 to 40 mg/m² weekly during RT or tri-weekly 80 to 100 mg/m² days 1, 22 and 43
- 8. Males or females 21 years or older
- 9. Karnofsky performance score (KPS) ≥ 70% (appendix E)
- 10. Screening laboratory assessments:
 - Hemoglobin ≥ 10g/dl

This document contains confidential information. It is intended solely for the use of the principal investigator, co-investigators, staff, appropriate institutional review boards or ethical committees, and other required regulatory bodies.

- White blood count ≥ 3500 cells/mm3
- Absolute neutrophil counts ≥ 1500 cells/ mm3
- Serum AST and ALT \leq 3 x ULN
- Calculated Creatinine Clearance ≥ 50 ml/min

• Negative pregnancy test (serum or urine)[#] performed 7 days before IMP administration

11. Females of childbearing potential[#] must confirm the use of an effective method of birth control during study participation and for 30 days following the last treatment with IMP. Acceptable methods of contraception for females include the following:

a) Double contraceptive methods including the use of either a male or female condom, a diaphragm or cervical cap associated with a spermicide, on top of one of the following:

- combined estrogen and progestogen containing hormonal contraception (oral, intravaginal or transdermal)
- Progestogen-only hormonal contraception associated with inhibition of ovulation (oral, injectable, implantable)
- Intrauterine device

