5.6 Investigational Medicinal Product Administration

Subjects will receive a mouth rinse package which will contain the following 2 components for the reconstitution of the mouth rinse suspension:

- AG013-DP powder or matching placebo in an aluminum sachet
- Reconstitution solution

A short summary of dose preparation is provided in Figure 2.

Figure 2 Summary of the different steps to reconstitute the mouth rinse suspension

Briefly, the SR needs to be added to the AG013-DP or Placebo, and shaken for at least 30 seconds to obtain a homogeneous white opaque suspension, ready for use.

Subjects will mix the study medication. Then, prior to the administration of the study medication, the patient will complete a 30 second cleansing rinse using bottled water. After

This document contains confidential information. It is intended solely for the use of the principal investigator, co-investigators, staff, appropriate institutional review boards or ethical committees, and other required regulatory bodies.

completing the cleansing rinse, subjects will shake the study medication to ensure reconstitution of the powder and then dose. Subjects will rinse with the suspension for 30 seconds three times each day using the assigned IMP. The suspension should then be expectorated into a sink or toilet. Subjects must have a witnessed dose; the first dose on Day 1 of CRT (prior to CT or RT whatever comes first). The witnessed dose should occur after the subject completes the OMDQ and prior to the subject leaving the clinic.

The IMP should be administered after meal however subjects should not eat, brush their teeth or use mouthwash for 15 minutes prior to and for 90 minutes after dosing. In addition, subjects should refrain from using processed sugars (e.g., candy, soft drinks, etc.) for 90 minutes after dosing with the study medication. Throughout participation in the study (i.e. till end of short term follow-up phase), subjects should be instructed not to drink alcohol within at least 4 hours after dosing with IMP or chew any gum other than the gum provided in the caries prevention kit (Section 5.15). Subjects should also be directed to only use the gum per the caries prevention instructions.

Detailed instructions for dose preparation and dispensing to subjects will be provided to the clinical site by the Sponsor or its designee.

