7.3 Active treatment Phase

7.3.1 Baseline (Day 1 of Chemoradiation therapy)

Prior to the first dose of CRT, the following observations and procedures will be completed:

- Obtain and record vital signs and body weight
- Determine KPS
- Provide and review instructions for completion of the daily diary that includes OMDQ responses; questions on IMP dosing, tolerability (taste, consistency and smell) and general quality of life, and analgesic medication use
- Have the OMDQ completed prior to the oral assessment
- Conduct OM assessment and record the WHO grade
- Record concomitant medications
- Record analgesia use for oral pain
- Record all AEs and SAEs that have occurred since ICF signature
- Record presence of prophylactic gastrostomy tube
- Provide caries prevention kit and give instructions for use
- Laboratory assessments (can be performed up to a day before IMP dosing)
 - CBC: WBC (cell count differential in %), hemoglobin, hematocrit, platelet count, RBC indices

This document contains confidential information. It is intended solely for the use of the principal investigator, co-investigators, staff, appropriate institutional review boards or ethical committees, and other required regulatory bodies.

- Chemistry: sodium, glucose, potassium, BUN, creatinine, phosphorus, calcium, alkaline phosphatase, LDH, AST, ALT, albumin
- Draw blood for biomarkers studies
- Draw blood for genetic responder/non-responder (for subjects who consent separately)
- Administer first dose of IMP (must be witnessed) prior to CT or RT whatever comes first

Administer RT and, if scheduled, CT; record the time of RT/CT administration

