To ensure that primary efficacy results are robust, sensitivity analyses will be performed using alternative methods for the analysis of duration of severe OM in both the ITT, mITT and PP populations. These methods will include calculations based on the number of days with grade 3 or 4 mucositis throughout the active treatment phase (from start of CRT until 14 days after completing CRT), and the use of various imputation strategies for gap days (i.e., days between twice weekly assessments). In particular, imputation of last observation carried forward and worst-adjacent values will be employed for subjects with missing or incomplete data.

Secondary Efficacy Endpoints:

Statistical methods for the calculation and analysis of secondary efficacy endpoints are provided below. For each endpoint, significance testing will evaluate the superiority of AG013 compared to placebo; two-sided tests will be used to reject the null hypothesis (no difference between groups) in favor of the alternative hypothesis (there is a difference between groups). All efficacy analyses will be performed for the mITT population and stratified by randomization factors (region, cisplatin regimen and HPV status). To control the experiment-wise Type 1 error rate at 5%, significance tests will be performed in the hierarchical order listed here.

Time to onset of severe OM: Time to onset of severe OM (WHO grade 3 or 4) will be calculated as the elapsed time (in days) from the start of CRT until the date of first OM assessment grade 3 or 4. Subjects who do not experience an event by the end of the OM assessment period will be censored on the date of last OM assessment. Subjects with no post-baseline OM assessments will be censored on Day 1. Kaplan-Meier estimation methods and the stratified log-rank test will be used to compare time-to-event distributions and test whether or not AG013 delays the onset of severe OM.

Incidence of severe OM: The incidence of severe OM (WHO grade 3 or 4) will be calculated as the number of subjects with at least one OM WHO grade 3 or 4, divided by the number subjects in the treatment group. Subjects with no OM assessments will be assumed to have severe scores. Subjects who die or withdraw without experiencing OM grade 3 or 4 will also be assumed to have severe scores. A stratified CMH test (general association statistic) will

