This document contains confidential information. It is intended solely for the use of the principal investigator, co-investigators, staff, appropriate institutional review boards or ethical committees, and other required regulatory bodies.

be used to compare proportions and test whether or not AG013 reduces the incidence of severe OM.

Duration of ulcerative OM: The duration of ulcerative OM (WHO grade 2, 3 or 4) will be calculated in a manner similar to duration of severe OM. That is, the duration of ulcerative OM will be calculated as the number of days from the onset of ulcerative OM (first time a WHO grade 2, 3 or 4 is observed) to the day when ulcerative OM has resolved (first time WHO grade 0 or 1 is observed after last WHO grade 2, 3 or 4). A similar imputation scheme will be used in the event that subjects die or withdraw prior to resolution of OM to grade 0 or 1. The stratified CMH test (with modified ridit scores) will be used to compare treatment groups and test whether or not AG013 reduces the duration of ulcerative OM.

Time to onset of ulcerative OM: Time to onset of ulcerative OM (WHO grade 2, 3 or 4) will be calculated and analyzed as described above for severe OM.

Incidence of ulcerative OM: Incidence of ulcerative OM (WHO grade 2, 3 or 4) will be calculated and analyzed as described above for severe OM.

Cumulative radiation dose to development of severe oral mucositis: Total cumulative dose of radiation (in Gy units) until the date of first severe OM (WHO grade 3 or 4) will be calculated for each subject and summarized by treatment group using descriptive statistics. Similarly, the cumulative radiation dose up to the first observed ulcerative oral mucositis (WHO grades 2-4) will be tabulated. The difference between treatment groups will be evaluated using the stratified CMH test, with modified ridit scores. This test will determine whether the AG013 group achieved a higher cumulative radiation dose before onset of severe OM, compared to the placebo group.

Patient-reported pain: The average of patient-reported mouth and throat soreness (MTS) scores, graded on a scale from 0 (no soreness) to 4 (extreme soreness), will be summarized by treatment group during each study week. The difference between treatment groups will be evaluated using the stratified CMH test, with modified ridit scores, to determine whether or not AG013 reduces pain.

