8.7.3 ANALYSIS OF OTHER SECONDARY EFFICACY ENDPOINTS

Cumulative radiation dose to development of severe oral mucositis: Total cumulative dose of radiation (in Gy units) until the date of first severe OM (WHO grade 3 or 4) will be calculated for each subject and summarized by treatment group using descriptive statistics in the mITT population. Similarly, the cumulative radiation dose up to the first observed ulcerative oral mucositis (WHO grades 2-4) will be tabulated. If a subject does not experience severe OM during the study, the full cumulative radiation dose will be used. The difference between treatment groups will be evaluated using the stratified CMH test (with modified ridit scores). This test will determine whether the AG013 group achieved a higher cumulative radiation dose before onset of severe OM, compared to the placebo group.

Patient-reported pain: The average of patient-reported MTS scores, graded on a scale from 0 (no soreness) to 4 (extreme soreness), will be summarized by treatment group during each study week as well as for the last 7 days of treatment in the mITT population.

The difference between treatment groups will be evaluated using the stratified CMH test (with modified ridit scores) to determine whether or not AG013 reduces pain.

Other Diary Outcomes: For other diary items: overall health, limited in swallowing, drinking, eating, talking and sleeping, overall soreness and diarrhea descriptive statistics will be produced for each treatment and by study week as well as for the last 7 days of treatment in the mITT population. However, no significance tests will be performed.

Analgesic use: Use of analgesics (parenteral, oral, or transdermal) to control oral pain will be examined by displaying number and percentages of subjects in the mITT population taking:

- Topicals such as viscous lidocaine
- OTC analgesics such as acetaminophen or ibuprofen
- PO opioids such as Vicodin or Percocet
- Parenteral opioids such as morphine or Fentanyl

Also, PO and Parenteral opioids will be combined to form a category for all opioids. Pvalues for all opioids and parenteral opioids will computed using the stratified CMH test (with modified ridit scores).

All the patient-level secondary endpoints will be listed together with the primary endpoint. Listings of radiation therapy data, OMDQ, and analgesics will be created as well.

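### The pain comparison makes no adjustment for the soreness score collected on Day 1 before dosing: the test stays valid, but some precision and protection against chance imbalance are given up

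*SAP*

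**What the plan says.** Average MTS (OMDQ Question 2, scored 0 to 4) "will be summarized by treatment group during each study week as well as for the last 7 days of treatment in the mITT population" (SAP 8.7.3). The difference between the arms is then to be "evaluated using the stratified CMH test (with modified ridit scores) to determine whether or not AG013 reduces pain". Protocol 10.5 specifies the same comparison, "evaluated using the stratified CMH test, with modified ridit scores, to determine whether or not AG013 reduces pain", and says efficacy analyses are "stratified by randomization factors (region, cisplatin regimen and HPV status"). Neither document gives the pain analysis a baseline covariate, a change score or a soreness stratum. SAP section 9, on departures from the protocol, does not mention the matter.

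A pre-treatment score is nonetheless scheduled. Protocol 6.3.2 has Question 2 completed daily from baseline. The Day 1 checklist in Protocol 7.3.1, all of it due before the first CRT dose, includes "Have the OMDQ completed prior to the oral assessment". Protocol 5.6 adds: "The witnessed dose should occur after the subject completes the OMDQ". Question 2 asks about the preceding 24 hours (Protocol Appendix C), so the Day 1 answer describes a wholly untreated period. SAP 8.2 defines baseline as the last assessment before first IMP, but the pain analysis does not use it. MTS is not among the baseline characteristics listed in SAP 8.6.1.

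**The concern.** Subjects may well start with different levels of soreness. Inclusion criterion 4 reads "Planned to receive either primary or post-operative CRT", so some will have had surgery and others will still have the tumor in place. Oral cavity and pharyngeal primaries are eligible, no criterion limits soreness at entry, and the Day 1 checklist already asks for analgesic use for oral pain. Surgical status is not a randomisation factor.

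If starting soreness predicts later soreness, variation that existed before treatment stays in the error term, and a chance difference between arms at Day 1 moves the pain comparison. With no baseline MTS table planned, a reader of the report might not see such a difference. The SAP uses this test to decide whether AG013 reduces pain, so the loss falls on a stated secondary endpoint.

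**Working it through.** **Inputs from the documents:** 80 per group, a 5-day difference, SD 10.8 days and two-sided 5% (SAP 6 and 8.1, all for the primary endpoint); about 200 enrolled (Protocol 4.1); 2×2×2 = 8 strata.

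**Assumed:** rho of 0.2, 0.3 and 0.4; a standardised pain effect of 5/10.8 = 0.463, borrowed from the primary endpoint because the documents give no SD or effect for pain.

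**1. The plan's own figure.** Normal approximation: 0.463 × √(80/2) = 2.93, and Φ(2.93 − 1.96) = 83.3%. The exact t-test gives 82.9%. The SAP states approximately 80%, so its figure is conservative. It concerns duration of severe OM and says nothing about pain.

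**2. Variance removed and equivalent subjects.** Adjustment removes a share rho² of the variance. The equivalent number of extra subjects is N × [1/(1 − rho²) − 1]. Approximate power with adjustment is Φ(2.93/√(1 − rho²) − 1.96), against 83.3% without.

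| rho | Variance removed | Extra subjects, N=160 | Extra subjects, N=200 | Approximate power |
|---|---|---|---|---|
| 0.2 | 4% | 6.7 | 8.3 | 84.8% |
| 0.3 | 9% | 15.8 | 19.8 | 86.6% |
| 0.4 | 16% | 30.5 | 38.1 | 89.2% |

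**3. Simulation of the actual test.** This used 160 subjects in 8 strata, 2,000 runs per setting, and a discrete 0 to 4 baseline score with about half the values at 0. Here rho is the correlation before scores are rounded to the scale.

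| rho | Stratified CMH | Rank-ANCOVA CMH | Gain (points) |
|---|---|---|---|
| 0.2 | 79.25% | 80.20% | 0.95 |
| 0.3 | 79.85% | 82.05% | 2.20 |
| 0.4 | 79.15% | 83.50% | 4.35 |

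These gains are smaller than step 2 implies. A coarse baseline score with many zeros carries less information than the linear formula assumes. With no treatment effect, rejection rates lay between 4.85% and 5.7% across both methods and every rho tried (0 to 0.6).

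**4. Effect of a chance imbalance.** With 80 per arm, the 95% limit for a baseline difference is 1.96 × √(2/80) = 0.31 SD. It shifts the unadjusted difference by rho × 0.31, which is 0.06, 0.09 and 0.12 SD. Against the borrowed 0.463 SD that is about 13%, 20% and 27%.

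**5. Why not a change score.** Its variance factor is 2(1 − rho), which exceeds 1 when rho is below 0.5. Approximate power would be 63.9%, 69.7% and 76.2%, worse than the 83.3% for the raw score. The useful correction is covariate adjustment.

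**The case against.** The strongest reply is that this is a preference about efficiency and that the plan contains no error. Randomisation makes the unadjusted test valid, the protocol and SAP agree on it, and it is the same rank test used for the primary endpoint. All of that stands.

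A reader might infer more than the documents support:

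- That the comparison is biased, or that an imbalance passes in full into the pain result. It does not: only the fraction rho carries over (step 4).
- That the pre-dose score is discarded altogether. SAP 8.2 makes the first IMP day Day 1, and study week is not defined for the averages, so the score may fall inside the Week 1 average. OMDQ data will also be listed. Neither amounts to adjustment.
- That 8, 20 and 38 subjects is the expected gain. Pain is analysed in the mITT population, so 200 is a ceiling.
- That wide baseline soreness is established. No baseline MTS distribution is given. The exclusions for oral infection, confounding lesions, unhealed extraction sites and active dental disease (Protocol 4.3) may narrow it.

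The consequence is also limited. Protocol 5.14 calls pain a key secondary endpoint, but SAP 5.2 and 5.4 place it outside the key secondary hierarchy. These points reduce the weight of the concern. They do not give a reason to leave a scheduled, pre-treatment predictor out of the test.

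**Conclusion.** The omission is real and modest in size. The planned test controls type I error. It forgoes some precision and leaves the result open to a chance difference in starting soreness, in proportion to rho. On the assumed range of 0.2 to 0.4, the variance removed is about 4% to 16%, equivalent to about 7 to 30 subjects at n=160. The simulated power gain runs from about 1 point at 0.2 through 2 at 0.3 to 4 at 0.4. The power figures rest on a borrowed effect size, and all the figures rest on a rho the documents do not supply. The gain is slight at 0.3 or below and worth having at 0.4 or above. The change is worth making because it is nearly free, not because the planned analysis is unsound.

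**What to change.** SAP 8.1 allows the statistical methods to be updated before database lock. By then:

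1. In SAP 8.7.3, specify stratified rank ANCOVA for each tested MTS average (each study week and the last 7 days of treatment). Within each stratum, rank the average and the Day 1 pre-dose MTS, regress the first on the second, and apply the CMH mean-score test to the residuals.
2. Exclude the pre-dose Day 1 score from the Week 1 average. Otherwise that outcome would be adjusted for part of itself.
3. Report baseline MTS by arm.
4. For a missing Day 1 score, use the stratum mean computed without regard to treatment. SAP 8.3 currently rules out imputation of this kind, so amend it for this covariate only.
5. Keep the unadjusted stratified CMH test as a supportive analysis, and record the change in SAP section 9.

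The cost is a few sentences of SAP text, a few lines of code and one more set of results, with no new data. The downside is little return if baseline scores cluster near 0 or rho is low. The choice must be fixed before unblinding, since deciding on adjustment afterwards would invite selective reporting.

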8.7.4 EXPLORATORY EFFICACY ENDPOINTS

Exploratory efficacy analyses will be conducted for the mITT population only. The effects of AG013 will be explored on the basis of the following:

Descriptive statistics will be presented for the incidence of severe OM (WHO grades 3 or 4) within subgroups receiving each of the following cumulative radiation doses: <=30 Gy, >30 and <= 40 Gy, >40 and <= 50 Gy, >50 and <= 60 Gy, and > 70 Gy. As with the secondary endpoint analysis, incidence will be defined as the proportion of subjects in each subgroup having at least one grade 3 or 4 OM assessment.

The distribution of OM severity grades at each visit will be provided for CTC and RTOG rating scales. These summary tables will display the number and percentage of patients per OM grade at each visit, by treatment group, for the mITT population.

For each subject, oral mucositis severity scores (WHO grades 0-4) at each time point will be used to calculate AUC using the trapezoidal rule. Average severity-by-time curves will

be generated and plotted for each treatment group, and compared using the Wilcoxon rank-sum test. Descriptive statistics for AUC values will be presented.

Incidence, duration and time to onset of grades 3 and 4 and grades 2, 3, and 4 OM as per NCI CTCAE and RTOG criteria will be analyzed separately, using the same methodology as described for the primary and secondary endpoints. Listings of NCI CTCAE and RTOG grades will be prepared, as well as listings of the calculated endpoints.

Frequency and duration of RT interruptions: The number of subjects in each treatment group with an unplanned break in RT during the 7- to 9-week regimen will be tabulated. Subjects with an interval of 5 days or more without an administration of RT, or who discontinue RT prior to completing the planned RT regimen, will be considered to have an unplanned break in RT. The duration of unplanned RT interruptions (in days) will also be summarized by treatment group using descriptive statistics. For subjects who prematurely discontinue RT, the time from the last dose of RT to the prescribed end date of the regimen will be used in the calculation.

All the RT data will be listed. Calculated values for the above listed endpoints will be listed separately.

The number of unplanned office visits, ER visits, hospitalizations, and non-prophylactic gastrostomy tube placements (US sites only) in each treatment group will be tabulated.

Listings of healthcare resource utilization data (US data only) will be created.

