1.1.2 Clinical Effects of Oral Mucositis

The severity of OM varies from superficial erythema, accompanied by soreness, to full-thickness mucosal ulcerations, necessitating parenteral narcotics for pain control (Scully et al., 2006). Among patients receiving myeloablative CT regimens or RT to the head and neck, OM is the most commonly cited bothersome adverse event (AE) associated with treatment (Rose-Ped et al., 2002).

The clinical impact of OM is profound, especially when ulceration is present. Even OM described as slight to moderate is associated with increased oral pain, weight loss, the need to modify diet, dehydration, and reduced performance status (Elting et al., 2007). Oral mucositis results in loss of critical functions, such as the ability to eat and to swallow, which can lead to dehydration, weight loss, and the need for nutritional support (e.g., gastrostomy tube placement). Furthermore, the ulcerations associated with OM are a frequent site of secondary infections and, in myelosuppressed patients, may act as portals for systemic bacterial spread (Reuscher et al., 1998). Treatment breaks prompted by patients' inability to tolerate the symptoms associated with OM compromise cancer therapy. And there is a strong association between OM and diminished quality-of-life (QOL) outcomes (Elting et al., 2008).

Besides its symptomatic toll, OM is associated with a number of negative health and economic outcomes, including increased analgesic and antibiotic use, number of febrile days, need for parenteral nutrition, prolonged length of hospital stay, and

This document contains confidential information. It is intended solely for the use of the principal investigator, co-investigators, staff, appropriate institutional review boards or ethical committees, and other required regulatory bodies.

increased resource use and associated cost. In granulocytic patients, mucositis is strongly associated with an increased risk of bacteremia and sepsis (Reuscher et al., 1998). Among patients treated for HNC, even mild OM results in more frequent hospitalization and breaks in treatment (Vera-Llonch et al., 2006).

Despite its frequency and significance, there is no approved intervention for RT-induced OM in HNC. Furthermore, currently there is a single agent approved as a treatment for OM, Kepivance[®], and its application is limited to OM associated with conditioning regimens prior to stem cell transplant for the treatment of hematologic malignancies.

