4.2.1 RADIATION THERAPY TREATMENT PLAN

Subjects will receive a continuous course of intensity-modulated radiotherapy with a minimum cumulative dose of 50 gray (Gy) and maximum dose of 72 Gy. Planned radiation treatment fields must include at least 2 at-risk sites for OM (maxillary or mandibular labial mucosa, right or left buccal mucosa, right or left ventral and/or lateral tongue, floor of oral cavity, or soft palate/tonsillar pillars) with each site receiving a total dose of \geq 50 Gy.

Radiation dose delivery will be clearly documented.

Changes in the radiation therapy plan will be allowed. However, the changes (example: dose delay, changes in the planned radiation dose or number of fractions) and the reason for the change should be clearly documented.

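### SAP 8.7.4 bands subjects by total radiation dose received, so its exploratory table does not show how much severe OM has occurred by 30, 40, 50 or 60 Gy (minor)

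*SAP*

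**What the plan says.** SAP 8.7.4 plans descriptive statistics for "incidence of severe OM (WHO grades 3 or 4) within subgroups receiving each of the following cumulative radiation doses". It forms the groups "within subgroups receiving each of the following cumulative radiation doses: <=30 Gy, >30 and <= 40 Gy, >40 and <= 50 Gy", then ">50 and <= 60 Gy, and > 70 Gy". There is no group above 60 and up to 70 Gy. Within each group, "incidence will be defined as the proportion of subjects in each subgroup having at least one grade 3 or 4 OM assessment". That definition does not refer to the dose reached when the grade 3 or 4 assessment was made. On the analysis set, the section says: "Exploratory efficacy analyses will be conducted for the mITT population only". SAP 8.1 has every analysis displayed by treatment arm and overall.

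The Protocol's eligibility rule (section 4.2) is planned IMRT "with a cumulative radiation dose of at least 50 Gy and maximum dose of 72 Gy", in single daily fractions of 2.0 to 2.2 Gy. SAP 4.2.1 repeats the range as a "minimum cumulative dose of 50 gray (Gy) and maximum dose of 72 Gy" and allows the radiation plan, including planned dose and number of fractions, to change during the study.

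Dose at onset appears elsewhere. SAP 8.7.3 computes each subject's cumulative dose to first severe OM, gives subjects without severe OM their full dose, and compares the arms with a stratified CMH test. It reports no proportions by dose threshold.

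**The concern.** The groups are bounded and do not overlap, and each has its own denominator, so a subject is classed by the total dose received. A subject whose severe OM begins at 36 Gy and who goes on to complete 72 Gy is counted in the band above 70 Gy. Nothing in the table records that onset came at 36 Gy.

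Total dose received is fixed only after randomisation, and the documents link it to the outcome. Protocol 1.1.2 says: "Treatment breaks prompted by patients' inability to tolerate the symptoms associated with OM compromise cancer therapy". SAP 7.4 counts a subject with less than 50 Gy as evaluable if the OM assessment reached grade 3 or more, so the plan foresees severe OM together with a dose shortfall. If severe OM makes early stopping more likely, the low bands are enriched with severe cases. The table could then suggest that lower doses carry more severe OM. By-arm figures within a band would also no longer compare groups formed by randomisation.

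**Working it through.** The plan states no figure for this analysis, so there is none to reproduce.

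**Step 1: which bands can a completed plan fall in?** The inputs are planned totals of 50 to 72 Gy and fractions of 2.0 to 2.2 Gy (Protocol 4.2). Whole-fraction totals fall as follows.

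| Fraction size | up to 30 | >30 to 40 | >40 to 50 | >50 to 60 | >60 to 70 (no band) | >70 |
|---|---|---|---|---|---|---|
| 2.0 Gy | 0 | 0 | 1 (25 × 2.0 = 50) | 5 | 5 | 1 |
| 2.1 Gy | 0 | 0 | 0 | 5 | 5 | 1 |
| 2.2 Gy | 0 | 0 | 0 | 5 | 4 | 1 |

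Apart from completers of exactly 50 Gy, anyone in the three lowest bands received less than any eligible plan. Adding the missing band above 60 and up to 70 Gy would be a separate repair and would not change this.

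**Step 2: how many subjects?** Protocol 4.1 enrols about 200 to obtain 160 evaluable. Under the Protocol's definition of evaluable (at least 4 weeks of IMP and at least 50 Gy), that leaves 200 − 160 = 40. If all 40 were below 50 Gy, there would be 20 per arm, or about 7 per arm in each of the three bands. This is a planning ceiling, not a forecast.

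**Step 3: how far can selection move the low-band figures?** Severe OM incidence is taken from SAP section 6: p = 0.75 on placebo and 0.50 on AG013. Two stopping rates are assumed, because the documents give none: a share s of severe cases and u = 0.03 of the others stop before 50 Gy, the same in both arms. No subject is assumed to have a plan of exactly 50 Gy.

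- Share in the low bands: L = p·s + (1 − p)·u
- Incidence in the low bands: p·s / L
- Incidence above 50 Gy: (p − p·s) / (1 − L)

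At s = 0.10, placebo gives L = 0.075 + 0.0075 = 0.0825, low-band incidence 0.075/0.0825 = 91%, and 0.675/0.9175 = 74% above. AG013 gives L = 0.05 + 0.015 = 0.065, low-band incidence 0.05/0.065 = 77%, and 0.45/0.935 = 48% above.

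| s | Share in low bands, placebo / AG013 | Low-band incidence | Incidence above 50 Gy |
|---|---|---|---|
| 3% | 3.0% / 3.0% | 75% v 50% | 75% v 50% |
| 5% | 4.5% / 4.0% | 83% v 63% | 75% v 49% |
| 10% | 8.25% / 6.5% | 91% v 77% | 74% v 48% |
| 15% | 12.0% / 9.0% | 94% v 83% | 72% v 47% |

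The low-band difference between arms falls from 25 points to 20.8, 14.0 and 10.4, although the treatment effect is the same in every row. The odds ratio stays at 3 (at s = 10%: 10 / 3.33), because stopping here depends on OM alone and not on arm.

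**Step 4: do the bands track dose at onset?** A one-group simulation held the onset curve fixed. Its assumptions were 75% incidence, onset at mean 40 Gy with SD 10, plans of 60, 66 or 70 Gy, and 5% stopping for other reasons. Only the share of severe cases who stop because of OM was varied.

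| OM-driven stopping | Band >30 to 40 | Band >40 to 50 |
|---|---|---|
| 0% | 24% | 52% |
| 5% | 63% | 82% |
| 10% | 75% | 89% |
| 15% | 81% | 92% |

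The true cumulative onset was 38% by 40 Gy and 63% by 50 Gy throughout. Each of these bands held about 1% to 5% of subjects. The proportion of all subjects with onset before radiotherapy ended was 72.3% in every row, because OM-driven stopping comes after onset.

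**The case against.** The best defence is that dose at onset is already analysed, at a higher rank. SAP 8.7.3 does so in the whole mITT population without conditioning on total dose, and it includes a test. That stands and limits the consequence. It does not fill the gap, because 8.7.3 gives no proportion affected by 30, 40, 50 or 60 Gy. The endpoint wording in Protocol 10.1.6 and SAP 5.6 also does not say that dose at onset is the aim. Reading it that way is an inference from the named thresholds.

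The item is also exploratory and descriptive, with no test within bands, and the small denominators will be visible. That stands too, and is why the point is minor.

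Four stronger readings are tempting, and the documents do not support them.

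- A reader might infer that the documents show mucositis lowering total dose. Protocol 1.1.2 speaks of breaks, and a break need not reduce the total. SAP 7.4 is closer support but gives no rate.
- A reader might take 91% v 77% as the expected result. It is one assumed pattern. If stopping is unrelated to severe OM, there is no distortion in this calculation.
- A reader might say the low bands contain only early stoppers. Subjects who complete a reduced plan, or exactly 50 Gy, fall there too.
- A reader might say incidence is counted over all follow-up. SAP 8.7.4 refers back to the secondary analysis, where 8.7.2 uses two windows: all follow-up, and first to last day of CRT. Neither window ties a case to its dose at onset.

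**Conclusion.** The point holds as a minor one about an exploratory table. The structural part rests on the text alone: subjects are grouped by total dose received, cases are counted regardless of dose at onset, and the three lowest bands lie at or below the smallest eligible plan. By-arm figures within those bands are conditioned on a post-randomisation variable that OM can affect, and the table does not report severe OM by dose reached.

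The size is uncertain. With 3% stopping among subjects without severe OM, low-band incidence runs from 75% v 50% (no distortion) to 94% v 83% as stopping among severe cases goes from 3% to 15%. These rates are assumptions. The calculation also assumes equal stopping behaviour in the two arms. A reader might infer that the efficacy conclusions are biased. They are not: no primary or key secondary analysis uses these bands.

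**What to change.** Replace the bands in SAP 8.7.4 with the proportion of all mITT subjects in each arm whose first WHO grade 3 or 4 assessment fell on or before the date on which delivered dose reached 30, 40, 50, 60 and 70 Gy. For subjects whose radiotherapy ended below a threshold, count onset up to the last fraction. Beside each proportion, show the number who ended radiotherapy below that threshold without severe OM. Report first onset after the last fraction in a separate row, since OM assessment continues into short-term follow-up when no further dose accrues.

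A Kaplan-Meier curve with delivered dose as the axis, censored at the last delivered dose, may be added as supportive. It is a different estimator from the simple proportion. It needs a note that censoring at an early radiotherapy stop may be informative, for example when painful grade 2 OM ends treatment.

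The cost is a paragraph of SAP text and one re-programmed descriptive table. The radiotherapy and OM dates are already needed for SAP 8.7.3. The downside is some overlap with that endpoint.
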